Key notes regarding study setting and design: Four community substance abuse treatment agencies have partnered with the research team for this study. These four agencies have 1-9 sites each that are scattered around Western Washington for a total 15 sites. Each site varies from 1-3 Intensive Outpatient Program (IOP) groups which run simultaneously. Each IOP has approximately 24-36 sessions of 2-3 hours each (72 hours total). Once they complete all sessions, the IOP restarts. New IOP clients enter the program at any time and stay till they have attended all 24 or 36 sessions. Thus, each Step in this Stepped Wedge design will be an entirely new set of clients.

Only one IOP for each site will be selected to be the focus of this study (Selected IOP). All client participants will be recruited and consented by research staff and the interventions (TAU vs. PARS) will be in the Selected IOP.

Within each Step, data collection will be as follows. Two weeks prior to the week Standard/PARS session is to be conducted in the selected IOP, research staff will connect with counselors at that site to (a) set up a plan for client recruitment and (b) have counselors complete online assessments themselves. One week prior to the Standard/PARS session, the research staff will come to the program 1-3x to recruit participants with the goal of recruiting all willing participants enrolled in that Selected IOP. Baseline assessments completed at recruitment. Follow-up assessments online or by phone two weeks, then one, three, and six months after recruitment.

Administrative Supplement: We will conduct a sub-study to culturally tailor PARS for use in Alaska Native and American Indian (ANAI) communities. This will be conducted in three ANAI communities with whom [name] and/or [name] are currently collaborating.

1.7 Intent. Check all the descriptors that apply to your activity. You must place an "X" in at least one box.

This question is essential for ensuring that your application is correctly reviewed. Please read each option carefully.

Descriptor
 1. Class project or other activity whose purpose is to provide an educational experience for the researcher (for example, to learn about the process or methods of doing research).
 2. Part of an institution, organization, or program's own internal operational monitoring.
 3. Improve the quality of service provided by a specific institution, organization, or program.

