Recent suicidal behavior or suicidal ideation is not an exclusion criterion in this study. (While it was in our pilot study, no participant was excluded on this basis.) The scope of chemical dependency counselor's practice in Washington State is to screen and refer acute suicidality to other professionals – often this means outside of the IOP program if a licensed mental health counselor or psychiatric provider is not available. Suicidality is not a static phenomenon – it waxes and wanes for the suicidal individual depending on their internal state and external circumstances. In addition, many individuals do not disclose their suicidality or their suicidality is not acute in while in IOP although it may have been before or after. These individuals are standardly part of IOP programs and they are part of the mission of PARS as are those who have never been suicidal but are at high risk by virtue of substance abuse history severe enough to be in treatment. Thus, all addiction clients regardless of suicidal thoughts or attempt history will be included in the study if they are in treatment at the time of recruitment. We have reviewed with our agency partners the expected incidence of acute suicide risk during a given IOP step. They report this is a rare event. Out of over 200 clients in 15 sites receiving IOP at any given time, they estimate that that 1-3 clients (~1%) are acutely suicidal and may have been referred out.

C5. Recruitment and Consent

The sites in this study vary from 1-3 IOP groups running simultaneously. Therefore, based on a consensus of the research team and community agency for that site, one IOP group in each site will be identified as the best fit for this study based on likely longevity of the counselor over the course of the study and engagement of that counselor with the study and interest in learning PARS. If this identifies more than one group, the decision will include the group with maximum attendance. As noted above, all counselors at the site will be trained in PARS (standard PARS training model) and multiple counselors will be trained to fidelity to assure PARS is administered on schedule to the identified group. Counselors may or may not administer PARS in the other IOP groups as decided by that site. This will not impact the study treatment.

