Primary outcome analyses. In the proposed stepped wedge design, 15 addiction treatment sites that initially provide TAU (Step 1) will be randomized to implement PARS beginning at one of five ensuing steps (Steps 2-6), 3 sites at a time. Participants recruited at each step will be assessed at points: baseline, post-treatment (information and attitudes only), 1, 3, and 6 months. The primary outcome analyses will be intent-to-treat analyses that include all participants, including those with incomplete follow-up data. The primary outcomes will be 1) knowledge about suicide, 2) maladaptive attitudes towards suicide, and 3) help-seeking behaviors. Each outcome will be evaluated in a separate generalized linear mixed model (GLMM)⁶⁰ to evaluate the effect of PARS program vs. Treatment As Usual on change in each outcome over time. The GLMM approach accounts for within-individual and between-group variance and is well-suited for the analyses of multisite, repeated measures data. A logit link function will be used to model dichotomous outcomes and a Gaussian link function when the outcome is relatively normally distributed.

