Moderation Analyses. We will examine whether individual-level factors (e.g., demographic characteristics, drug and alcohol use, depression, physical and mental health functioning, treatment engagement) moderate the effect of the PARS program. To evaluate these individual-level moderators, the primary outcome analyses above will be extended to include the main effect of the moderator and its interactions with Treatment, Time, and the Treatment by Time interactions. Each moderator will first be evaluated in a separate model to ascertain whether any differences in treatment effects were associated with individual level factors. A follow-up model will evaluate the moderators simultaneously in a single model. The statistical test of moderation will be the three-way Treatment by Time by Moderator interactions.

[figure not shown]
Mediation Analyses. Secondary mediation analyses will examine whether baseline to post-intervention 1) increases in knowledge about suicide and 2) decreases in maladaptive attitudes about suicide will mediate the effect of PARS vs. TAU help-seeking behaviors. The mediation analyses will be conducted using multilevel structural equation modeling.⁶¹ Robust standard error estimates and corrected model fit statistics (e.g., Satorra-Bentler statistic) will be utilized to accommodate non-normally-distributed dependent variables in the model.⁶² Each mediator will first be evaluated in a separate model. Figure 2 illustrates the basic autoregressive regression model⁶³ that will be used to assess longitudinal mediation of the effect of intervention on 1-, 3-, and 6-month help-seeking behavior. An indicator variable for Step will be included as a covariate if the effect of step is statistically significant in the primary outcome analyses. The model will incorporate random effects for site and individual to account for the clustered design (i.e., repeated measures nested within individuals, nested within site). The mediated effect ($a_1 * b_5$) and its confidence interval will be obtained using bootstrap resampling, as recommended for testing indirect effects.⁶⁴ (Note, arrows on upper right side of mediator and outcome boxes represent error terms.)

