Dose Response Analyses. Exploratory analyses will evaluate whether Time (i.e., number of steps) in the intervention phase is associated with improved outcomes in successive steps. The following regression equation depicts the basic dose response model for each outcome: $OUTCOME_{t>0, is} = b_0 + b_1 BL_OUTCOME_{is} + b_2 TAU_TIME_{is} + b_3 PARS_TIME_{is} + u_{0s} + r_{0is} + e_{tis}$, where t indexes the assessment, i indexes the individual, and s indexes the site. In this model, Time will be centered at the beginning of the intervention phase, such that Time = 0 will correspond to the step in which PARS was implemented at a particular site. Time will be coded as a piecewise linear function representing two phases: 1) the TAU phase: the change over time in outcomes during the control period and the 2) PARS phase: a “deflection” term representing the change in slope from the TAU phase following the implementation of PARS. To account for the cluster-randomized design, a random effect for site (u_{0s}) will be included to model the correlation of individuals from the same site. To account for the repeated assessments, a random effect for participant (r_{0is}) will be included to model the correlation of observations within the same individual. The statistical test of the dose-response effect will be the magnitude and statistical significance of the slope of Time during the intervention period.

Power Analysis. We base our power analysis on a stepped wedge design³⁵ evaluating the difference in the rate of help-seeking behavior at month 1 (post-intervention) among those receiving PARS vs. TAU. Based on our pilot study of PARS, we anticipate a 15.6% baseline rate of help seeking behavior, which we expect to increase to 28.1% at post-intervention (1-month) follow-up. Based on the proposed stepped wedge design in which 10 individuals are recruited per site in each of the 6 steps ($N = 900$), we will have 89% power to detect the 12.5% difference in the rate of help-seeking behavior. Assuming 25% fewer participants ($N = 675$, 7.5 individuals per site per step), due to under-recruitment and/or attrition, there will still be 80% power to detect an intervention effect. This represents a conservative estimate of statistical power as the full longitudinal model will leverage data from all participants, including those with incomplete follow-up data.

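### Aim 3 mediation test: the bootstrap has no stated resampling unit, and resampling either level of the planned model (15 sites, or clients) declares mediation too often when PARS has not moved the mediator

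*SAP*

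**What the plan says.** SAP C.7, Mediation Analyses, plans a multilevel structural equation model for each mediator (knowledge, attitudes). The mediated effect is the product a1*b5, and "its confidence interval will be obtained using bootstrap resampling, as recommended for testing indirect effects". The section gives no resampling unit, interval type or number of resamples. The hierarchy it does state is "repeated measures nested within individuals, nested within site", with random effects for site and individual. Its robust standard errors are there for non-normal outcomes, not for clustering. Step enters only if it was significant in the primary analysis.

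The design around it:
- SAP C.7, Primary outcome analyses: "15 addiction treatment sites that initially provide TAU (Step 1) will be randomized to implement PARS", three sites at a time.
- SAP C.7, Power Analysis: "10 individuals are recruited per site in each of the 6 steps".
- SAP C5, Recruitment and Consent: "one IOP group in each site will be identified as the best fit for this study".
- Protocol 1.6: "each Step in this Stepped Wedge design will be an entirely new set of clients".

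Each of the 15 × 6 = 90 site-by-step cells is therefore one group of about 10 new clients who shared one PARS or TAU session.

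**The concern.** The a1 path is the effect of a session that is assigned by site and delivered to a group. Its sampling error comes from how site-by-step cells differ, not only from how clients differ. PARS combines teaching with group discussion (SAP C3), and Protocol 5.2 names one influence that acts on a whole site at one step: a client death by suicide may change responses there. A session-level component is plausible, yet the mediation model has no term for it.

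A reader following the stated hierarchy would resample sites or clients. Resampling clients treats people who shared a session as independent. Resampling sites keeps the clustering but relies on 15 units, three per sequence, with no small-sample correction.

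At stake is the mechanism conclusion. The SAP's Innovation section (item 4) says the mediator result may decide whether PARS is refined towards attitudes, knowledge or both. A false mediated effect would point that work at a mediator PARS did not change.

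**Working it through.** **1. The plan's own figure.** No power is stated for mediation. The nearest figure is that "we will have 89% power to detect the 12.5% difference in the rate of help-seeking behavior", with 80% at N = 675. For a stepped wedge with I = 15 sites and T = 6 steps, Var = I·s²(s² + T·t²) / [(IU − W)s² + (U² + ITU − TW − IV)t²]. Here s² is the variance of a cell mean and t² the site variance.
- From the design figure: U = 45, W = 495, V = 165, so IU − W = 180 and the second bracket is 630.
- Mean rate (0.156 + 0.281)/2 = 0.2185, so s² = 0.2185 × 0.7815/10 = 0.01708.
- Site CV 0.14 gives t² = (0.14 × 0.156)² = 0.000477 (ICC about 0.003), SE = 0.0389, z = 0.125/0.0389 = 3.21, and power = Φ(3.21 − 1.96) = 89.5%. At 7.5 per cell it is 80.0%.

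The stated figures reproduce, but only with a small site variance that the SAP does not give. At ICC 0.05 they would be 78.2% and 67.5%. So the documents supply no usable ICC, and those below are assumptions.

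**2. True spread of a1.** Take a standardised mediator, site ICC 0.05 and session ICC 0.05. Then s² = 0.05 + 0.90/10 = 0.14. The same formula gives Var = 15 × 0.14 × (0.14 + 0.30) / (180 × 0.14 + 630 × 0.05) = 0.924/56.7 = 0.0163, so SD = 0.128. Simulation gave 0.129.

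**3. What each bootstrap reports.** In that simulation the mean bootstrap SE was 0.094 for clients (0.094/0.129 = 0.73, 27% short) and 0.123 for sites (5% short).
- Clients: 1.96 × 0.73 = 1.43, and a normal tail beyond ±1.43 is 15%. Simulated: 15.8%.
- Sites: 1.96 × 0.953 = 1.87. A normal tail gives 6.2%; a t tail on 13 df gives 8.4%. Simulated: 8.6%. Most of the excess is what few sites would produce.

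**4. False mediation at a1 = 0, nominal 5% (%).** Percentile intervals; values in order of session ICC.

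| b, trials per setting | Session ICC | Sites | Clients | Monte Carlo, session-level SE | Whole sessions |
|---|---|---|---|---|---|
| 0.3, 600–900 | 0 / 0.02 / 0.05 | 9 / 8 / 10.5 | 4.5 / 6 / 14 | 4–6 | – |
| 0.4, 2,000 | 0 / 0.02 / 0.05 / 0.10 | 8.6 / 8.6 / 8.6 / 8.8 | 9.1 / 11.8 / 15.8 / 22.0 | – | – |
| 0.4, 400 | 0 / 0.02 / 0.05 | 8 / 9 / 9.5 | 8 / 10 / 16 | 4 / 4 / 3.5 | – |
| 0.3, 1,000 | 0 / 0.02 / 0.05 / 0.10 | 8.4 / 6.9 / 7.7 / 6.6 | – | – | 3.5 / 3.4 / 3.8 / 3.8 |
| 0.35, 600 | 0 / 0.02 / 0.05 | 8–9 | 8 / 10 / 14 | 4.5–6.5 | about 5 |

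Simulation error is about 0.6 points at 8.6% with 2,000 trials and about 1 point in the smaller runs.

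**5. Variations, b = 0.4.**
- Bias-corrected intervals, session ICC 0.05: sites 9.1%, clients 17.0%.
- Binary outcome, session ICC 0.05: 9.0% and 16.5%. Step omitted: 8.8% and 14.7%.
- Resampling sites within randomisation group: 15.7–16.5%.
- Parametric draw from the planned model's own standard errors: 6.0 / 11.5 / 16.4% at session ICC 0 / 0.05 / 0.10.
- Requiring both paths to be significant, with a1 tested on the 90 cell means with site and step terms (90 − 15 − 5 − 1 = 69 df): 4.6–5.7%.
- Two-stage resampling (sites, then clients): 1.6 / 2.7 / 4.2%, but power about 0.5 against about 0.8.
- Both paths zero: 0.7% for sites and for clients. With a1 = 0.5 and b = 0: 6.7–8.6% (sites) and 7.0–8.5% (clients) for a continuous outcome; 7.1% and 5.0% for a binary one.

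**The case against.** **The SAP does not say clients or sites, so perhaps this is only missing detail.** Part of this stands. A reader might infer that no bootstrap can work with 15 sites and that naming the unit would not help. The documents and figures do not support that: the SAP excludes no scheme, and resampling whole site-by-step sessions held the level. But a session is not a level of the stated hierarchy, which leads an analyst to the two units that fail. A parametric draw from the planned model fails too, so detail alone is not enough; the session has to enter the analysis.

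**Session differences as the cause.** A reader might infer that both bootstraps fail because sessions vary. That is true of client resampling. Site resampling shows no trend with session ICC, and its excess is there at zero.

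**The session ICC may be overstated.** Mediation runs through change from a baseline taken in the same group a week earlier. Cohort differences, including the effect of an earlier suicide at the site, would be largely in that baseline. This stands as a limit on the client figures: at ICC 0.02 they are 6–12%. It does not touch the site figures. The figure defining a1 and b5 is not shown, and the simulations use one follow-up and a linear model.

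**The consequence is narrow.** Knowledge and attitudes are primary outcomes, so whether PARS moved each one is tested separately, and the pilot reported change in both. This stands. The gap also shrinks under a real effect in one run: at a1 = 0.4 and session ICC 0.05, coverage was 91% (clients), 93.5% (sites) and 96% (Monte Carlo). Another run gave 83%, 91% and 96%.

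**Conclusion.** The concern holds in this form. The SAP rests Hypothesis 2 on a bootstrap whose unit is unnamed, in a model whose only levels are site and individual, and neither level keeps a nominal 5% when b is non-zero and a1 = 0. Site resampling gives about 8–9% (6.6–10.5% across runs) because there are 15 sites. Client resampling gives about 5–9% without session variation, 14–16% at session ICC 0.05 and 22% at 0.10.

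These sizes rest on assumed ICCs, assumed paths (b from 0.3 to 0.4), two-sided 5%, percentile intervals and a simplified model. The direction was the same across the runs, except that client resampling was at 4.5% in one run with no session variation. A reader might infer that mediation is over-declared in general, or that the trial's main results are affected. Neither follows: the test is conservative when both paths are zero, and Aim 3 is secondary, so the primary tests are untouched. It is worth correcting before analysis, with medium confidence in the exact sizes.

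**What to change.** Amend SAP C.7, Mediation Analyses, as follows.

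1. Add a site-by-step (session) random effect to the a1 model, and always include step instead of making it depend on significance.
2. Base the interval for a1*b5 on session-level uncertainty, naming one method:
   - **Monte Carlo interval.** Draw a1 and b5 from their estimated sampling distributions, using the session-level standard error of a1 with small-sample degrees of freedom, and take the 2.5th and 97.5th percentiles of the product. False mediation was 3.5–6.5% across runs. It works directly with the pooled estimates from the 10 imputed data sets. The session-level standard error restores the level, not the Monte Carlo draw itself.
   - **Bootstrap of whole site-by-step sessions.** False mediation was 3.4% to about 5%. The SAP would then also need to state the interval type, the number of resamples and how the bootstrap combines with multiple imputation.
3. State that clients alone, or whole sites alone, will not be resampled.

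Cost: SAP wording only, with no change to data collection. Intervals are slightly wider. At a1 = 0.4, b = 0.3 and session ICC 0.05, Monte Carlo power was 0.82 against 0.84 (sites) and 0.90 (clients) in one run, and 0.765 against 0.80 and 0.905 in another. That is a loss of about 2–4 points against sites and 8–14 against clients. Session resampling gave 0.78 against 0.83 for sites in the run that compared them.

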This study will use a stepped wedge design as shown in Figure 1. This design is recommended for studies in which it is beneficial to randomize at the site rather than individual level.³⁵⁻³⁷ Such is the case in this study, as randomization at the individual level would not be feasible with our community partners, who are enrolling clients and placing them in groups based on many complex reasons including client schedules, IOP group schedules and openings, and a myriad of agency guidelines and regulations. Such a study would require conducting PARS and usual care in a research clinic setting—which is the opposite of our goal. PARS was developed in community settings and its effectiveness in those settings is key. Once it was determined that randomization would be at the site level, both clustered randomized and stepped wedge designs were considered.^{35,37-44} While both have benefits, the stepped wedge has the advantage of measuring dose-response (delay) effects. Furthermore, its primary disadvantage (that more assessment points were required)^{35,40,42} was not determined to be a problem for the research team or community partners, as participants would complete the same assessments regardless of stepped wedge or cluster randomization.

In the proposed study, there will be six steps. Steps will be 6 months each to assure sufficient time for all data collection to occur given that some IOP programs are as long as 12 weeks and sites will vary as to which session PARS replaces in their IOP curricula. In each of the six steps of the study, baseline assessments will be conducted the week before that selected session at that site. For instance, Site A might replace session 8 with PARS but Site B might replace session 14, so baseline assessments will be conducted in week 7 at Site A and week 13 at Site B. (Data collection methods for baseline assessments described in Procedures below.) This will assure that the follow-up assessments reflect the period after PARS is administered while allowing the natural variation in IOP curriculum that is inevitable with 15 community partner sites.

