As per the stepped wedge design (see Figure 1), the 15 sites will be randomly assigned to 5 groups of three sites each. At Step 1, all sites will be in the TAU condition. The 5 groups will then be randomly assigned to begin PARS at one of the subsequent 5 steps (i.e., Step 2-6). Once beginning PARS, they will continue to administer PARS through the end of Step 6. Thus, three sites per step will begin administering PARS—until by Step 6, all sites are administering PARS.

[name], stepped wedge design expert (as can be seen in his Biosketch), has reviewed and approved our design (as noted in his Letter of Support) and is available for consultation as needed.

C4. Participants.

Setting. Participants (N=900) will be recruited from 15 community treatment sites in Washington State from the four treatment agencies that are our community partners in this study. As can be seen from their Letters of Support, our community partners are enthusiastic about PARS and see both the program and the study design

as feasible and acceptable. Sites represent urban and rural areas in Washington as well as representing sites primarily funded by private insurance and self-pay and those primarily paid by Medicaid.

Inclusion and Exclusion Criteria

Inclusion Criteria

1. Enrolled client in one of the community treatment settings
2. Over 18 years of age
3. Ability to understand written and spoken English

Exclusion Criteria

1. Any clinical medical/psychiatric condition, severity of that condition, or life situation that in the opinion of the counselors or Drs. [name] or [name] would compromise safe and voluntary study participation (e.g., psychosis, custody conflict).

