*The following regression equation depicts the basic model for each outcome: $OUTCOME_{tis} = b_0 + b_1 STEP2_{is} + b_2 STEP3_{is} + b_3 STEP4_{is} + b_4 STEP5_{is} + b_5 STEP6_{is} + b_6 SETTING_{is} + b_7 PARS_{is} + b_8 MONTH1_{tis} + b_9 MONTH3_{tis} + b_{10} MONTH6_{tis} + b_{11} (PARS_{is} * MONTH1_{tis}) + b_{12} (PARS_{is} * MONTH3_{tis}) + b_{13} (PARS_{is} * MONTH6_{tis}) + u_{0s} + r_{0is} + e_{tis}$, where t indexes the assessment, i indexes the individual, and s indexes the site. In this model, each outcome is regressed on Step, Setting (Rural vs. Urban), Treatment (PARS vs. TAU), Time (in months), and the Treatment by Time interaction. The effect of Step will be coded into contrasts of Step 1 against each subsequent step (i.e., Step 2 vs 1, Step 3 vs 1, etc.). The effect of Time will be coded into contrasts of baseline (BL) against each post-baseline assessment (i.e., BL vs. 1 month, BL vs. 3, BL vs. 6 months). To account for the cluster-randomized design, a random effect for site (u_{0s}) will be included to model the correlation of individuals from the same site. To account for the repeated assessments, a random effect for participant (r_{0is}) will be included to model the correlation of observations within the same individual. The statistical test of the treatment effect will be the magnitude and statistical significance of the Treatment by Time interactions. Comparable analyses will be used for exploratory aims with suicidality and substance use.*

Since this study will be carried out at 15 sites, there is the potential for site-specific effects. We anticipate intervention effects to be comparable across all clinics since they are all serving similar client populations and have counselors with comparable levels of experience and training. To verify that treatment effects are comparable across site, preliminary outcome analyses will incorporate indicator variables for site and their interactions with the treatment effects. A likelihood ratio test will be used to compare the models with and without site-specific effects. If the likelihood ratio tests reveal differences in treatment effect by site, these

site-specific parameters will be retained in the final analyses, otherwise they will be excluded.

Secondary Analyses

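### The exploratory dose-response model has no PARS on/off term, so an immediate, stable PARS effect will be read as growth or as waning, depending on which coefficient is tested

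*SAP*

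**What the plan says.** SAP C.7, Dose Response Analyses, writes each follow-up outcome as b0 + b1 × baseline outcome + b2 × TAU_TIME + b3 × PARS_TIME, plus a random site effect, a random participant effect and residual error. Time is centred within site: "Time = 0 will correspond to the step in which PARS was implemented at a particular site". PARS_TIME is described as a deflection, a "term representing the change in slope from the TAU phase following the implementation of PARS". The test is then given as follows: "The statistical test of the dose-response effect will be the magnitude and statistical significance of the slope of Time during the intervention period".

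The primary model in the same section has both a PARS main effect (b7) and indicators for Steps 2 to 6. The dose-response equation has neither, and nothing elsewhere in the SAP or protocol adds them.

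The analysis serves Exploratory Aim 4, whether outcomes improve the longer a clinic has been running PARS. In C3 (Stepped Wedge Design), the choice over a parallel cluster design is supported by the statement that "the stepped wedge has the advantage of measuring dose-response (delay) effects".

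**The concern.** PARS is a single session, and the SAP's power case is an immediate rise in help-seeking at one month. A level shift between the last TAU cohort and the first PARS cohort is thus the result the sponsor expects. A piecewise line without a level term must be continuous at the switch, so it represents such a shift by sloping. The baseline covariate cannot absorb it, because baseline is taken the week before the session.

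The tested quantity is also unclear. Under the deflection coding, the slope during the PARS phase is b2 + b3, while b3 alone is the change in slope. The two are biased in opposite directions, so one stable benefit could be reported as growing or as waning.

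A second, separate gap is that without Step terms nothing in the model represents calendar time as such. Drift common to all sites can then pass for a dose effect.

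**Working it through.** **Inputs from the SAP.** In C3, "the 15 sites will be randomly assigned to 5 groups of three sites each"; there are six steps, with crossover at Steps 2 to 6. C.7 (Power Analysis) gives 10 clients per site per step (N = 900), or 7.5 (N = 675), and help-seeking of 15.6% vs 28.1%. Alpha, ICC and outcome SD are not stated. I assume two-sided 0.05, ICC 0 to 0.3 and unit residual SD unless noted.

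**The plan's own figure.** The SAP gives no operating characteristics for the dose-response test, so I checked the stated 89% and 80% power for the primary comparison. The Hussey-Hughes variance is Iσ²(σ² + Tτ²) / [(IU − W)σ² + (U² + ITU − TW − IV)τ²], with I = 15, T = 6, U = 45, W = 495, V = 165. Take σ² = 0.2185 × 0.7815 / 10 = 0.01708 and an assumed site CV of 0.15, so τ = 0.0234. The SE is then 0.0391, z = 0.125/0.0391 = 3.20, and power is 89.3%, or 79.8% at 7.5 per cell. CVs of 0.10 and 0.20 give 90.3%/80.9% and 88.0%/78.4%. The layout and inputs are therefore read correctly.

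**Effect size.** 0.125 / √(0.2185 × 0.7815) = 0.30 SD. On the log-odds scale it is 0.749.

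**Bias by hand at ICC 0.** Let the truth be 0 under TAU and 1 under PARS, with no growth. The number of groups observed at T = −5, …, 4 is 1, 2, 3, 4, 5, 5, 4, 3, 2, 1. With intercept a, TAU slope s1 and PARS slope s2, the normal equations are:

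- 30a − 35s1 + 20s2 = 15
- −35a + 105s1 = 0
- 20a + 50s2 = 20

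The solution is a = 21/31, s1 = 7/31 = 0.226 and s2 = 4/31 = 0.129. The change in slope is s2 − s1 = −3/31 = −0.097. All three slope quantities are truly zero.

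**Other ICCs** (GLS on the 90 site-step cells, per unit of immediate effect d):

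| ICC | PARS-phase slope (SE) | Change in slope (SE) |
|---|---|---|
| 0 | +0.129 (0.0344) | −0.097 (0.052) |
| 0.05 | +0.136 (0.0365) | −0.099 (0.053) |
| 0.1 | +0.138 (0.0370) | −0.100 (0.053) |
| 0.3 | +0.139 (0.0374) | −0.100 (0.053) |

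For a 12.5-point jump this is about +1.6 to +1.7 points per step for the PARS-phase slope (12.5 × 0.129 to 0.139), and about −1.2 to −1.25 for the change in slope.

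**False significance at 0.30 SD, ICC 0.**

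- PARS-phase slope: z = 0.30 × 0.129/0.0344 = 1.125, so P(Z > 1.96 − 1.125) = 20%. It is 20% across ICC 0 to 0.3.
- Change in slope: z = −0.30 × 0.097/0.052 = −0.56, so P(Z < −1.96 + 0.56) = 8%. It is falsely positive in under 1%.

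**Sensitivity of the 20%.**

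- 16% at 7.5 per cell.
- 27% with unit total SD at ICC 0.3.
- About 14% if half of an ICC of 0.1 is site-by-step variance (assumed).
- For assumed effects of 0.1, 0.2, 0.4 and 0.5 SD: 6%, 11%, 32% and 46-47%.
- With three correlated follow-ups per client (assumed within-person share 0.4), the two-sided rate is 31-32%.

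**Logit check.** Simulation with a flat log-odds effect of 0.749 and one follow-up per client used 8000 runs at ICC 0 and 3000 each at 0.05, 0.1 and 0.3, with site variance treated as known. The PARS-phase slope was falsely positive in 16-17% and the change in slope falsely negative in 12-15%. With PARS and Step terms added, the rates were 2.4-2.9% positive and 2.3-3.2% negative.

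**Calendar drift of x per step.** The PARS-phase slope picks up 0.56x to 1.0x before baseline adjustment. If baseline drifts equally and its coefficient is 0.3 to 0.7 (assumed), the leak is roughly 0.56 × 0.3 = 0.17x to 1.0 × 0.7 = 0.70x. The change in slope picks up −0.05x to 0.

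**After repair.** Adding PARS alone makes both slope biases exactly 0, but the PARS-phase slope still carries 0.50x to 0.97x of linear drift. With PARS and Step terms, bias and drift leak are both 0.

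**The case against.** The best counter-argument is that the only definition given for the PARS-phase coefficient is a change in slope. If b3 is what is tested, a false claim of growth occurs in under 1% of trials, and linear drift is almost wholly absorbed by TAU_TIME. The larger figures belong to the other reading. That is right, but the SAP's sentence on the test permits the other reading, and under the b3 reading a stable benefit is still wrongly called waning in 8% to 15% of trials.

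The rates are also assumption-driven. Help-seeking would be analysed with a logit link if dichotomised, where 16-17% is the better figure. An effect that fades by 3 and 6 months would give a smaller average jump and a lower rate. This stands as a caution about size, not about direction.

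A smaller repair exists: keep TAU_TIME, add PARS and test b3. It removes the immediate-effect bias and linear drift, with an SE of 0.053 to 0.055 SD per step. Step terms are then needed only for drift that is not linear.

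Finally, the analysis is exploratory, the equation is called basic, and C.7 plans plots to inform how time is parameterised. None of these supplies a level term. The aim is named, and the ability to study dose-response is one of the reasons given for the design.

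**Conclusion.** The dose-response model is misspecified for the effect the SAP itself expects. With an immediate, non-growing effect d, the PARS-phase slope is biased by +0.13d to +0.14d per step and the change in slope by about −0.10d. These follow from the layout and held at every ICC tried. For maladaptive attitudes, where lower is better, the signs reverse but the direction relative to benefit does not.

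At the SAP's help-seeking effect, the chance of a false growth signal from the PARS-phase slope is about 16% to 20%, and 27% in the least favourable one-follow-up case shown at that effect, against 2.5%. The chance of a false waning signal from the change in slope is 8% to 15%. These rates assume two-sided 0.05, ICC 0 to 0.3, no calendar trend and no site-by-step variance.

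The primary PARS vs TAU tests are untouched. The model should be corrected because, as written, the answer to Exploratory Aim 4 could be wrong in either direction.

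**What to change.** Replace the equation with: follow-up outcome = baseline value + Step indicators + PARS (0/1) + PARS_TIME + random site and participant effects. PARS_TIME is 0 under TAU and counts 0 to 4 steps since the site started PARS. State that the coefficient of PARS_TIME is the dose-response test. A site-by-step random effect is optional.

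If the piecewise form is preferred, keep TAU_TIME, add PARS (0/1) and name b3 as the test, noting that this protects against linear drift only.

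The cost is SAP wording and some precision; no new data are needed. With the recommended form, the SE of the slope rises from 0.034-0.037 SD per step (PARS-phase slope as planned) to 0.042 at ICC 0, 0.052 at 0.05, 0.055 at 0.1, 0.058 at 0.3, or 0.060 with site fixed effects. If half of an ICC of 0.1 is site-by-step variance, it rises from 0.045 to 0.063. The precision given up came from assuming that outcomes do not jump when PARS begins and that there is no separate calendar trend.
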